16.1.4 Missing Data Sensitivity Analyses of Primary Efficacy Endpoint

Three sensitivity analyses will be implemented to explore different types of missing data approaches, as defined in [Section 16.1.2](#). For purposes of multiple imputation, SAS default common risk differences (as opposed to Newcombe) will be generated in order to capture risk difference standard errors.

16.1.4.1 Multiple Imputation Under MAR

Any missing component scores of MMS at the planned assessments will be imputed using multiple imputation under MAR. MAR assumes the missing value is independent of unobserved outcomes given observed data (i.e., participants with missing RB subscores can be modeled based on participants with observed RB subscores) ([Rubin 1987](#)).

Fully Conditional Specification (FCS) with predictive mean matching via PROC MI will be used in a “Just Another Variable” (JAV) approach in which all longitudinal variables are put into a “wide format” dataset ([Bergland 2015](#), [Bergland 2018](#)).

Variables with potentially missing values at post-baseline visits include SF, RB, ES, Geboes index score, absolute lymphocyte count (ALC), CRP, and PGA. These variables are continuous, and after multiple imputation per-participant responder values (‘Y’ or ‘N’) will be derived for the primary endpoint for every multiply-imputed dataset.

Variables with no missing values allowed are the randomization stratification factors, prior UC treatment failure of oral 5-ASA only (participant had inadequate response, loss of response, or intolerance to previous treatment with oral 5-ASA and did not have an inadequate response, loss of response, or intolerance to any other previous UC medication), and all of the previously mentioned continuous variables at baseline. If a participant has missing baseline values in any of these variables, the participant will be excluded from multiple imputation.

The following steps will be implemented:

Step 1:

Regardless of the arbitrary missing data pattern (i.e., non-monotone or monotone), a FCS method with predictive mean matching for continuous variables will be used to impute the missing data at all timepoints. The FCS method allows for separate conditional distributions for each imputed variable. The predictive mean matching approach creates a regression model using parameters sampled from the posterior distribution and then a predicted value for each missing value is computed. The missing value is replaced by randomly selecting an observation from a set of ‘k’ values that are the closest predicted values to the missing predicted value. Missing data imputation will be performed using the SAS PROC MI procedure.

Natural logarithm will be applied to ALC and CRP prior to multiple imputation. The number of imputations will be 40 and is based on a projected overall dropout rate of 10% and relative efficiency of > 99%. A separate imputation model will be used for each treatment group.

Refer to [Section 26](#) (Appendix V) for the order of variables and timepoints in the model as well as sample PROC MI code.

Step 2:

For each of the 40 imputed datasets at Induction Week 13, participants will be classified as responder or non-responder based on the criteria specified in Section 16. For each dataset, the proportion of responders will be calculated. For endpoints requiring MMS, MMS will be recomputed by summing the scores of ES, SF, and RB.

Step 3:

The PROC FREQ code given in [Section 16.1.3](#) will be applied to the 40 multiply-imputed datasets, resulting in 40 sets of CMH chi-square p-values, Newcombe risk differences, and CMH odds ratios.

Step 4:

PROC MIANALYZE requires sample statistics to have approximately normal distributions. The following table describes transformations applied to the three output statistics prior to handling with PROC MIANALYZE ([Ratitch 2013](#)):

Table 5. Transformations Prior to Using PROC MIANALYZE

Statistic	Transformed Value	Transformed Standard Error or Standard Deviation
Risk Difference ($p_1 - p_2$)	Identity	Identity
Odds Ratio ($\text{Odds}_1 / \text{Odds}_2$) †	$\ln(\text{Odds}_1) - \ln(\text{Odds}_2)$	$[\ln(95\% \text{ UCL}) - \ln(95\% \text{ LCL})] / (2 * 1.96)$
CMH Test Statistic ("VALUE") ††	$[(\text{VALUE}/df)^{(1/3)} - (1 - 2/(9 * df))] / ((2/(9 * df))^{(1/2)})$	1.0

† After application of PROC MIANALYZE, the results are back-transformed to the original scale

†† This Wilson-Hilferty transformation yields test statistics having an approximate normal distribution with standard deviation of 1.0. The multiply-imputed CMH p-value is obtained by computing one-sided t-statistic p-values after application of PROC MIANALYZE.

Refer to [Section 26](#) (Appendix V) for variable ordering, PROC MI code, sample SAS transformation code, PROC MIANALYZE code, and post-processing code.

It is noted there could be certain adjustments due to unexpected data issues after unblinding treatment. All post-unblinding modifications to the multiple imputation model or approaches to address missing data will be described in the CSR.

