████████████████████		X			X		X	X	
PK blood sampling ^x		X	X	X	X		X	X	X
████████████████████		X					X	X	

Study Procedures	Screening (4 weeks)	Induction Treatment Period (13 weeks)						Early Termination/ Follow-Up Period	
		7-day Dose Titration						ET Visit ^b	1-Week & 2-Week Follow-Up Visits ^b
Study Visit ^a	Visit 1	Visit 2 ^a	Visit 3	Visit 4	Visit 5	Visit 6 ^a	Visit 7		
Study Day	Day -28 to 0	Day 1	Day 8	Day 29	Day 57	Day 71	Day 92		
Window (days)			+ 2	± 3	± 3	± 3	± 3		
Study Week		Week 0	Week 1	Week 4	Week 8	Week 10	Week 13		
EFFICACY									
Endoscopy ^y	X						X	X	
eDiary ^z	X	X	X	X	X	X	X	X	
Mayo Clinic score ^{aa}		X					X	X	
Physician's Global Assessment		X		X	X		X	X	
Colonic biopsy ^{bb}	X						X	X	
IBDQ ^{cc}		X					X	X	

Abbreviations: ALT = alanine aminotransferase; AST = aspartate aminotransferase; β-hCG = beta-human chorionic gonadotropin; BP = blood pressure; DLCO = diffusing capacity of the lungs for carbon monoxide; ECG = electrocardiogram; EDC = electronic data capture database; eDiary = electronic diary; ET = Early Termination; FEV1 = forced expiratory volume in 1 second; FVC = forced vital capacity; HBV = hepatitis B virus; HCV = hepatitis C virus; HIV = human immunodeficiency virus; HR = heart rate; IBDQ = Inflammatory Bowel Disease Questionnaire; MMS = modified Mayo score; OCT = optical coherence tomography; PK = pharmacokinetics; RB = rectal bleeding; SF = stool frequency; TB = tuberculosis; [REDACTED] ULN = upper limit of normal

- a. All assessments scheduled for Visit 2 will be performed prior to study drug administration, unless otherwise indicated. All visits beyond Visit 2 may be virtual/hybrid visits (see Section 8.2). Visit 6 is planned as a phone call visit. Assessments scheduled for Visit 7 may be performed within 7 days prior to the date of visit.
- b. All participants who discontinue the study prematurely will be asked to return to the clinic for the ET visit, and the 1-Week Follow-Up and 2-Week Follow-Up visits after the last dose of study treatment. If the ET visit is ≥ 1 week after the last dose of study treatment, the 1-Week Follow-Up visit is not required; however, the 2-Week Follow-Up visit should be scheduled and completed. In the unlikely event that the ET visit is ≥ 2 weeks after the last dose of study treatment, the 2-Week Follow-Up visit is not required.

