6. DETERMINATION OF SAMPLE SIZE

Approximately 189 eligible participants will be randomized in the study. The study is powered to show superiority of VTX002 60 mg to placebo with respect to clinical remission at Week 13.

Based on literature data review, the expected proportion of clinical remission at Induction Week 13 is 28% for VTX002 60 mg and 8% for placebo (Sandborn 2016; Sandborn 2020). Under these assumptions, and with a 1:1 randomization ratio, two-group chi-squared test, and two-sided significance level of 5%, a sample of 57 participants per treatment group will be sufficient to achieve at least 80% power. Adding a 10% inflation for dropouts results in 63 participants per treatment group and 189 participants in total.

All sample size calculations were conducted in SAS 9.4.

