Table 6. Planned Primary and Key Secondary Analyses

X = VTX002 60 mg vs Placebo

Y = VTX002 30 mg vs Placebo

Endpoint	Primary Analysis with Stratified CMH (FAS)	Key Secondary Analyses with Stratified CMH ^b (FAS)	Section 16.1.4 Missing Data Sensitivity Analyses (FAS: MAR MI, CR MI, Tipping Point)	Section 16.1.5 Sensitivity Analysis (FAS)	Section 16.1.6 Supplementary Analyses (mFAS, PP Sets)	Section 16.1.7 Sensitivity Analyses (FAS)
Primary endpoint – Clinical Remission	X ^a Family 1	Y Family 4	X, Y	X	X, Y	X, Y
Key Secondary Endpoints						
Endoscopic Improvement		X: Family 2 Y: Family 5	X, Y		X, Y	X, Y
Symptomatic Remission		X: Family 2 Y: Family 5	X, Y		X, Y	X, Y
Histologic Remission		X: Family 3 Y: Family 6	X, Y		X, Y	X, Y
Endoscopic improvement – Histologic Remission		X: Family 3 Y: Family 6	X, Y		X, Y	X, Y

^a Serves as primary analysis gatekeeper for testing all Key Secondary Analyses with Stratified CMH

^b The collection of Key Secondary Analyses with Stratified CMH subject to a truncated Hochberg multiplicity adjustment to control the family-wise Type 1 error rate at $\alpha=0.05$. [Figure 3, Section 10.3](#) presents a flow chart demonstrating how this is to be done.

CMH = Cochran-Mantel-Haenszel; CR = copy reference; FAS = Full Analysis Set; mFAS = modified Full Analysis Set; PP = Per Protocol set; MI = multiple imputation; MAR = missing at random

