17.2.3 Summaries

For tabulation purposes, values below assay validity cutoffs will be set equal (e.g., if 1.112 mmol/L is the assay validity lower bound, a reported value of LDL-C < 1.112 mmol/L is set equal to LDL-C = 1.112 mmol/L prior to rounding) and values above assay validity cutoffs will be set equal (e.g., if 13.9 mmol/L is the assay validity upper bound, a reported value of LDL-C > 13.9 mmol/L is set equal to LDL-C = 13.9 mmol/L prior to rounding).

Four general sets of laboratory data summaries will be prepared: Induction Treatment Period, LTE, OLE, and the entire study. Safety Set will be used for induction treatment summaries and Safety-ET Set for LTE/OLE summaries.

Values, change from baseline, and percent change from baseline will be summarized descriptively, by visit, for each treatment group, and only central laboratory data will be tabulated.

- Summary Tables
 - Summary tabulations will only be prepared for central laboratory data using international system (SI) units
 - The normalized assay results (ALC, ANC, and CRP; see [Sections 17.2.1 and 17.2.2](#)) will be summarized separately from all other assay results and [REDACTED]
 - Fecal calprotectin (FCP) will only be summarized separately for [REDACTED]. [REDACTED] FCP will not be pooled, except for shift table purposes. See [Section 10.5](#) for clinically meaningful cutoffs applicable to FCP, regardless of central laboratory.
 - For the non-normalized assay results other than FCP, eGFR and hematology and serum chemistry data will be considered separately and will each be summarized [REDACTED] Visit windowing will be used to associate laboratory data with study visits – see [Section 9.6 Table 3](#).
- Shift Tables
 - Shift tables will include both central and local laboratory data whenever possible.
 - Normalized assay results (ALC, ANC, and CRP) will be considered only on a pooled basis
 - All non-normalized assay results, including FCP and eGFR, will be presented both separately for each central laboratory and also on a pooled basis
 - Shift tables (number and percentage) from baseline to every post-baseline visit will be presented
 - Shift tables for the change in laboratory results interpretation (e.g., flags such as ‘Normal’ vs ‘Low’ vs ‘High’ or ‘Abnormal, clinically significant’ vs ‘Abnormal, not clinically significant’ vs ‘Normal’) from baseline to every post-baseline visit and worst post-baseline visit in Induction Treatment Period

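### The MAR multiple-imputation model (SAP 16.1.4.1 and Table 11) is too large for arm-specific fitting, disagrees with the rest of the SAP on its variables, and has a baseline-exclusion rule at odds with its FAS label

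*SAP*

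**What the plan says.** SAP 16.1.4.1 imputes missing component scores by fully conditional specification with predictive mean matching, on a wide dataset, with 40 imputations. On the unit of fitting it says: "A separate imputation model will be used for each treatment group". It names the post-baseline variables as SF, RB, ES, Geboes, ALC, CRP and PGA, log-transforms ALC and CRP, and refers to Appendix V for the variables and their order. Table 11 in that appendix also contains log FCP.

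The stratification factors, the oral 5-ASA failure indicator and the baseline values of the continuous variables must be complete: "If a participant has missing baseline values in any of these variables, the participant will be excluded from multiple imputation". SAP Table 6 labels the missing-data sensitivity analyses "FAS: MAR MI, CR MI, Tipping Point" and plans them for both doses, on the primary and all four key secondary endpoints.

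On the data behind two of the terms, Protocol Table 1, footnote a, says "Visit 6 is planned as a phone call visit", and SAP 17.2.3 says "FCP will not be pooled, except for shift table purposes". The PROC MI code in Appendix V is redacted.

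**The concern.** Four features do not fit together.

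- **Size.** Fitted by arm, the model has nearly as many parameters as participants, so the matching that is meant to use each participant's history becomes largely noise.
- **ALC at Visit 6.** Predictive mean matching draws from observed values. A visit with no scheduled sample gives it almost nothing to draw from.
- **FCP.** The SAP models FCP separately by laboratory in the repeated-measures analysis (Sections 16.4 and 18) because the assays differ in major ways. Table 11 enters it with no laboratory term.
- **Baseline exclusion.** A participant with an observed Week 13 outcome but, say, no baseline CRP is excluded from imputation. Step 3 runs the analysis on the imputed datasets, and the readable text does not say whether or how such a participant re-enters.

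At stake is whether this analysis can be run as prespecified. Section 16.1.4.1 allows adjustment of the imputation model for unexpected data issues after unblinding, and 26.1.1 allows the variable order to change after lock. It is better to correct foreseeable faults now.

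**Working it through.** **Sample size (SAP Section 6).** The assumed remission rates are "28% for VTX002 60 mg and 8% for placebo", with two-sided alpha 0.05 and 80% power. The mean rate is 0.18.

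n = [1.96 × √(2 × 0.18 × 0.82) + 0.8416 × √(0.08 × 0.92 + 0.28 × 0.72)]² / 0.20² = (1.065 + 0.442)² / 0.04 ≈ 56.7, so 57. The power at 57 is 0.802, as the SAP prints. Then 57 × 1.10 = 62.7, so 63 per arm, as stated. At the projected 10% dropout, 63 × 0.90 = 56.7, or about 57, have Week 13 data.

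**Number of imputations.** 1 / (1 + 0.10/40) = 0.9975, which agrees with the stated relative efficiency above 99%.

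**Table 11 count.** Items run from 1 to 44 with no item 20: strata and 5-ASA failure 4, ES 2, Geboes 2, PGA 4, ALC 7, FCP 5, CRP 5, SF 7, RB 7. Total 43.

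**Residual degrees of freedom.** With k variables, each regression has k − 1 predictors plus an intercept, so df = n − k. The inflation of prediction variance for a new observation, relative to residual variance (Gaussian predictors, p = k − 1), is (n+1)(n−2) / [n(n−p−2)].

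| Model | k | df at 63 | df at 57 | Inflation at 57 |
|---|---|---|---|---|
| Table 11 | 43 | 20 | 14 | (58×55)/(57×13) = 4.30 |
| Without ALC Visit 6 | 42 | 21 | 15 | 4.00 |
| Also without FCP | 37 | 26 | 20 | 2.95 |
| Proposed (see fix) | 13 | 50 | 44 | (58×55)/(57×43) = 1.30 |

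Deleting the two faulty sets of terms therefore does not cure the size problem on its own.

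**ALC at Visit 6.** Items 13 to 19 are seven entries running from Visit 1 to Visit 7, which requires Visit 6. The FCP and CRP lists skip it. Protocol Table 1 has no hematology at Visit 6. The SAP Table 3 window for Visit 6 is Days 64 to 81. On-schedule Visit 5 samples fall on Days 54 to 60. Visit 7 samples, even taken 7 days early, fall on Day 89 − 7 = 82 or later. Only off-schedule, unscheduled or early-termination samples can map to Visit 6.

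**Leverage on the result.** About 6 of 63 per arm would be imputed. If they were imputed at 28% when the truth is 8%, the arm rate moves 6/63 × 20 = 1.9 points. With 3 imputed it moves 0.95.

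**Illustrative simulations (assumed data models).**

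- With 63 per arm and about 10% MAR dropout, the imputed ES ≤ 1 rate among the missing was 12 points too high with 42 predictors and 2 too high with 10. On the arm rate, 12 × 0.10 = 1.2 points.
- A similar scenario in two arms, with rates of 45% and 15%, shifted them by 1.4 and 1.2 points, a net 0.2 on the difference.
- A different data model (63 in one arm, 17% dropout, true response 44%) gave an arm bias of −0.4 points (SE 0.26) and root mean square error 2.1 for 42 variables, against 0.05 and 1.4 for 11 variables.

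The sign of the bias depends on the assumed data. In both data models the larger model did worse.

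**The case against.** The strongest reply is that little depends on this analysis. The primary method is non-responder imputation, and MAR imputation is one of three sensitivity analyses. The tipping-point analysis spans 0 to 100% response in each arm without using Table 11. Rescue therapy, discontinuation for worsening or a UC adverse event, and a missed Week 13 endoscopy in those eligible are non-responses under imputation too (Appendix VIII), so many of the sicker dropouts are never given an imputed outcome. All of this stands and limits the size of the problem.

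Several stronger readings are tempting, and the documents do not support them:

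- *The analysis is biased.* The simulations disagree in sign, and the treatment difference moves little.
- *The Visit 6 lymphocyte count is never collected.* It is unscheduled, and its presence is inferred from the numbering of an abbreviated list. Stray samples could map there.
- *Participants are certainly lost from the FAS.* The text excludes them from imputation and is silent on re-entry. The number is unknown and could be zero, since ES, SF, RB and ALC also feed eligibility. Gaps in baseline CRP, PGA or Geboes, or in SF and RB that cannot be derived from the eDiary, are more plausible.
- *The SAP forbids pooling FCP in any model.* Its statements concern summaries and the repeated-measures models. The same reasoning applies here, but the rule is not written for imputation.
- *The final model will be chosen with knowledge of treatment.* The SAP only permits adjustments and requires them to be described in the CSR.

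Two technical cautions also stand. With the code redacted, it cannot be confirmed that all 43 variables enter every regression, although no smaller set is stated. And the inflation factors multiply different residual variances: under the first simulation's correlations, absolute prediction variance was 0.68 against 0.25 with the ten strongest predictors, a ratio of about 2.7 rather than 4.30/1.24 = 3.5.

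**Conclusion.** The point holds as one of instability and internal inconsistency. If all listed variables enter each regression, the arm-specific models have 14 to 20 residual degrees of freedom. One term has almost no possible donors, five FCP terms conflict with the SAP's own variable list and its handling of the two laboratories, and the baseline rule is unreconciled with the FAS label. The expected effect is extra noise and an arm-rate shift of about 1 to 2 points, in no established direction. This rests on 10% missing data and the assumed models above. If 0 to 10% of participants lacked a baseline value, 63 to 57 per arm would remain in the imputation; the documents give no rate. The primary conclusion is not threatened, but the faults are visible now and should be corrected before unblinding.

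**What to change.** Before unblinding, amend 16.1.4.1 and Table 11:

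1. Delete ALC at Visit 6 and all FCP terms.
2. Let the fully conditional specification impute missing baseline covariates, so that every participant in the FAS efficacy analysis stays in. Participants with baseline MMS = 4 remain outside, as elsewhere in the SAP.
3. Prespecify a smaller per-arm model: the three stratification factors, ES at baseline and Week 13, and RB and SF at baseline, Week 4, Week 8 and Week 13 (3 + 2 + 8 = 13 variables). For the histologic endpoints add Geboes at baseline and Week 13 (15 variables, 42 residual df at 57). The Week 4 scores matter: without them, anyone leaving before Week 8 would be imputed from baseline data alone.
4. Align the copy-reference list in 16.1.4.2 with this model. It currently omits Geboes, although Section 16.2 applies the method to histologic endpoints.

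The cost is SAP wording and programming. PGA, CRP, the remaining ALC values and the other RB and SF visits no longer inform the imputation, and participants who leave before Week 4 are still imputed from baseline data.

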16.1.4.2 Multiple Imputation with Copy Reference

Missing data will also be explored assuming an MNAR approach. MNAR assumes the missing values depend on unobserved outcomes even after accounting for the observed data. Therefore, participants cannot be modelled based on participants with observed data, and more assumptions are needed. Copy reference is a type of MNAR approach where each missing value for participants in the treatment group will be imputed using observed data in the placebo group, and missing values for participants in the placebo group will be imputed under the MAR approach.

The following steps will be implemented:

Step 1:

Step 1 (a):

Intermittent missing data (before discontinuation from study) at each scheduled visit will be imputed, separately for each treatment group, under the MAR assumption using a multivariate normal imputation model and the Markov Chain Monte Carlo (MCMC) method with multiple chains. The number of imputations will be 40. The resulting data will have a monotone missing data pattern. The imputed data will be used together with observed data to impute post-discontinuation missing values.

Step 1 (b):

Only after Step 1 (a) is completed, the remaining monotone missing data after discontinuation will be imputed using the FCS predictive mean matching method based on data from the placebo group only. The RB, SF, ES, and PGA subscores, stratification variables, a binary variable indicating if a participant is a treatment failure, and biomarker measurements (ALC, R CRP, log-transformed) at each planned visit will be included in the imputation model.

Step 2:

Same as Step 2 described in [Section 16.1.4.1](#).

Step 3:

Same as Step 3 described in [Section 16.1.4.1](#).

Step 4:

Same as Step 4 described in [Section 16.1.4.1](#).

16.1.4.3 Tipping Point Analysis

A tipping point approach based on multiple imputation of Visit 7 Week 13 responses with respect to the primary endpoint will be used². This will be an MNAR-based imputation approach in

² <https://www.pharmasug.org/proceedings/2023/SD/PharmaSUG-2023-SD-069.pdf>

which direct Bernoulli simulation is used to evaluate the robustness of the obtained primary efficacy results with respect to various assumed response rates in each treatment arm.

The following steps will be implemented:

Step 1:

Participants not contributing observed RB, SF, and ES at Visit 7 Week 13 will be assumed to have primary efficacy response rates that vary according to the following thirty-element lists:

VTX002 60 mg: $p_{VTX} \in \{0\%, 2\%, 4\%, \dots, 30\%, 35\%, 40\%, \dots, 95\%, 100\%\}$

Placebo: $p_{PBO} \in \{0\%, 2\%, 4\%, \dots, 30\%, 35\%, 40\%, \dots, 95\%, 100\%\}$

Step 2:

- a. Consider all possible combinations of primary efficacy response rates. This yields 900 pairs of response rates.
- b. Fix attention to a specific pair of response rates. An example of such a pair would be ($p_{VTX} = 14\%$, $p_{PBO} = 35\%$).
 - i. Imputation #1: Assign responder or non-responder status to each participant not contributing observed RB, SF, and ES at Visit 7 Week 13. This will be done, per participant, by drawing $N=1$ random draws from a Binomial distribution having an appropriate probability from the response rate pair. An example of such a random draw would be generating $X_i \sim \text{Bin}(n=1, p_{PBO} = 35\%)$ for each i , where i indexes all placebo participants not contributing observed RB, SF, and ES at Visit 7 Week 13.
 - ii. Repeat until 40 total imputations have been generated
- c. Repeat 2b until all possible pairs of response rates have been handled.

Step 3:

Same as Step 3 described in [Section 16.1.4.1](#).

Step 4:

Same as Step 4 described in [Section 16.1.4.1](#).

Results will be plotted as a heat map on a two-dimensional plot with axes corresponding to the assumed primary efficacy response rates applied to each treatment group respectively, and different colors will be used to represent the magnitude of the 2-sided p -values corresponding to analysis with each combination of delta values. The clinical interpretation about the plausibility of the assumptions underlying the tipping point will be provided in the CSR.

